4.1 Inclusion Criteria

- Adult patients > 18 years of age
- Receiving deceased donor kidney transplant
- Pre-transplant Ejection Fraction (within past 18 months) > 50%
- Intraoperative or postoperative distributive shock (as described above) requiring vasopressor support

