The study drug will be provided by La Jolla Pharmaceuticals for this study but they are not the study sponsor or providing any other financial support. Drug distribution will be managed by the Investigation Drug Service (IDS) at UI Health who has the capacity to retain all of the study drug in appropriate temperature-controlled settings. IDS will be used as this is a novel medication, not yet on formulary at UIHHSS, and this is a research investigation. They will maintain and dispense the medication for each kidney transplant in which subjects have consented in the event that vasopressors are required. Additionally, the medication will be ordered via Cerner/EPIC as a study medication and will be programmed into the Alaris pumps to be dosed via the dosing protocol listed above. Ang II (Giapreza) will not be used outside of the study protocol at our institution and will only be available under the electronic study order. Verifying pharmacists will be in-serviced regarding the study protocol and will be aware that this medication is only available and should be dispensed under the study order and as such not used in other contexts.

FOR STUDIES THAT COLLECT EXISTING OR PROSPECTIVE DATA

Health and laboratory data will be extracted manually from the electronic medical records (i.e. Cerner or Epic) for both arms of the study. Data will be prospectively captured over the course of 3 months after study initiation (i.e. using Ang II (Giapreza) for vasopressor management during kidney transplant) for the pilot. The data will be collected and input into a Redcap database for analysis. Data analysis will be performed using Spss.v25 computer software. Data collection will include the variables below.

Baseline characteristics:

-Age (years of age at the time of transplant)

- -Gender (M/F)
- -Race
- A) White
- B) Black
- C) Asian
- D) Hispanic
- E) Other
- -Weight (kilograms at time of transplant)
- -Height (centimeters at time of transplant)
- -Body mass index (kg/m² at time of transplant)
- -Duration of time on hemodialysis (years)
- -Donor baseline serum creatinine (mg/dL)
- -Warm/cold ischemia time (hours)
- -KDPI
- -Baseline systolic/diastolic/mean arterial pressure (mmHg)
- -Baseline heart rate (HR)
- -Comorbidities
- A) Hypertension
- B) Hyperlipidemia
- C) Heart failure with preserved ejection fraction
- D) Arrhythmias
 - -Atrial fibrillation
 - -Other
- E) Peripheral vascular disease
- F) Coronary artery disease
- G) Pulmonary hypertension
- H) Diabetes

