Patients will be monitored according to standard monitoring for patients in the peri-operative transplant and collection of ADE will focus on those found in clinical studies using Ang II (Giapreza). The safety endpoints that will be captured will include: incidence of intraoperative arrhythmias for those who receive study drug intraoperatively (confirmed via EKG, flowsheet, or note documentation), incidence of postoperative arrhythmias occurring while receiving study drug postoperatively (confirmed via EKG, flowsheet, or note documentation), incidence of digital or other peripheral/visceral ischemia occurring during hospitalization for kidney transplant (as noted in chart documentation), incidence of venous or arterial thrombosis occurring during the hospitalization for kidney transplant (captured by ultrasound or other diagnostic imaging), incidence of thrombocytopenia while receiving study drug (as defined as platelet count < 50,000), incidence of post-operative fungal infections prior to discharge (as documented by the clinical care team), incidence of delirium while receiving study drug (as documented by the clinical care team), incidence of insulin infusion utilization while receiving study drug, pH values in the ICU at 24hrs, 48hrs, and 72hrs (if available). All of the noted safety variables above are routinely monitored for as part of ICU care.

Data Management

All patients that provide informed consent and receive Ang II (Giapreza) will have their data extracted. These patients will be considered included and associated with an alpha-numeric code that is linked to their medical record number (MRN). This list will be kept in a password protected Excel file on the primary investigator's computer stored on the H drive behind the University firewall on the primary investigator's password protected computer in a locked office. It will be available only to the co-investigators. Lastly, all data collected will not contain PHI and will be stored in Redcap.

All patients that provide informed consent but DO NOT receive Ang II (Giapreza) will be considered a screening failure and NO data will be extracted and they will not be associated with an alpha-numeric code linked to their MRN.

Records retention:

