11.0 DATA AND SAFTY MONITORING

The study drug will be given by FDA approved dosing and used within label as perioperative hypotension (when systematically addressed as noted above) is a form of distributive shock. As with all FDA approved medications, adverse events are reported. Patients will be monitored according to standard monitoring for patients in the perioperative transplant and collection of ADE will focus on those found in clinical studies using Ang II (Giapreza). The safety endpoints that will be captured will include: incidence of intraoperative arrhythmias for those who receive study drug intraoperatively (confirmed via EKG, flowsheet, or note documentation), incidence of postoperative arrhythmias occurring while receiving study drug postoperatively (confirmed via EKG, flowsheet, or note documentation), incidence of digital or other peripheral/visceral ischemia occurring during hospitalization for kidney transplant (as noted in chart documentation), incidence of venous or arterial thrombosis occurring during the hospitalization for kidney transplant (captured by ultrasound or other diagnostic imaging), incidence of thrombocytopenia while receiving study drug (as defined as platelet count < 50,000), incidence of post-operative fungal infections prior to discharge (as documented by the clinical care team), incidence of delirium while receiving study drug (as documented by the clinical care team), incidence of insulin infusion utilization while receiving study drug, pH values in the ICU at 24hrs, 48hrs, and 72hrs (if available). All of the noted safety variables above are routinely monitored for as part of ICU care.

The researchers will assess relatedness of the event to the study drug and will make every attempt to obtain enough information about the event to do so. Relationship of any AE to the use of study drug will be based on available information, using the following definitions:

Not Related: Another cause of the event is most plausible; and/or a clinically plausible temporal sequence is inconsistent with the onset of the event relative to initiation of study drug; and/or a causal relationship is considered biologically implausible.

Possibly Related: An event that follows a reasonable temporal sequence from administration of the Ang II (Giapreza) and in the investigators estimation follows a response pattern to the drug, but that could readily have been produced by a number of other factors.

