Probably Related: An event that follows a reasonable temporal sequence from administration of the Ang II and there is a biologically plausible mechanism for Ang II (Giapreza) to cause or contribute to the AE and the event could not be reasonably explained by the known characteristics of the participant's clinical state.

For reporting purposes, both 'Possibly Related' and 'Probably Related' will be considered **Related**.

Adverse events will also be graded by severity according to CTCAE criteria.

- -Grade 1: Mild; Asymptomatic or mild symptoms; clinical or diagnostic observations only; intervention not indicated.
- -Grade 2: Moderate; Minimal, local or noninvasive intervention indicated; limiting age-appropriate instrumental activities of daily living.
- -Grade 3: Severe; Medically significant but not immediately life-threatening; hospitalization or prolongation of hospitalization indicated; disabling; limiting self-care activities of daily living.
- -Grade 4: Life-threatening consequences; urgent intervention indicated.
- -Grade 5: Death related to AE.

Given this is a clinical trial a Data Safety Monitoring Board (DSMB) will be established. This board will be composed of two Critical Care Pharmacists ([name] and [name]) with intimate knowledge of Ang II (Giapreza), vasopressors, Ang II (Giapreza) safety endpoints and no relationship to the conduct of the trial. This DSMB will review the safety endpoints collected above after 5, 10, 15, and 20 subjects are enrolled. They will be provided a Safety Summary Report for the allotted number of patients with "Relatedness" and Grading of captured ADE as described above.

Study Halting Criteria: For existing participants study drug will halt dosing immediately until further safety analysis and assessment by the DSMB can be completed and no further enrollment will take place until approved by the DSMB. The halting criteria are as follows:

- Two participants experience the same Grade 4 adverse event considered related to study drug
- 20% of the participants at time of analysis experience the same Grade 3 adverse event
- One participant experiences a Grade 5 AE considered related to study drug

Study can be restarted if the DSMB says it is okay to continue.

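### The arrhythmia and insulin-infusion safety endpoints do not require an event that is new after the first dose, so pre-existing conditions can enter the reported incidence

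*Combined protocol and SAP*

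**What the plan says.** The safety data points in section 6.0, repeated in section 11.0, include three relevant endpoints:

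- "incidence of intraoperative arrhythmias for those who receive study drug intraoperatively"
- "incidence of postoperative arrhythmias occurring while receiving study drug postoperatively"
- "incidence of insulin infusion utilization while receiving study drug"

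Arrhythmia may be confirmed from an EKG, a flowsheet or a note. None of the three definitions mentions new onset, worsening or change from baseline.

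The baseline characteristics in section 6.0 include "D) Arrhythmias", subdivided into atrial fibrillation and other, and diabetes by type. No rule connects these fields to the scoring of the endpoints. The cardiac inclusion criterion in section 4.1 is "Pre-transplant Ejection Fraction (within past 18 months) > 50" per cent. The exclusions in section 4.2 contain no arrhythmia, diabetes or insulin item.

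Section 3.0 evaluates the secondary objective, safety, through the incidence of common adverse events. Section 11.0 adds a relatedness assessment, a CTCAE grade, DSMB reviews after 5, 10, 15 and 20 subjects, and halting criteria.

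**The concern.** An incidence endpoint should count events that arise after exposure. As worded, an insulin infusion that was already running when the study drug began meets the insulin endpoint. An operating-room arrhythmia that preceded the drug meets the intraoperative arrhythmia endpoint. A chronic rhythm charted on a flowsheet during the infusion could be entered under the postoperative one.

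The study treats one cohort of 20 patients. Section 6.0 refers once to two arms when it describes data extraction, but the design defines no comparator group. Nothing in the study would therefore show how much of an observed rate was present before the drug. At stake are the published safety incidence, its consistency between chart abstractors, and possibly one halting criterion.

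**Working it through.** **Step 1. Compare the three definitions with the start of drug.**

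| Endpoint | Limited to time on drug? | New event required? | Pre-drug status recorded? |
|---|---|---|---|
| Intraoperative arrhythmia | No, only to patients dosed intraoperatively | Not stated | Comorbidity history only |
| Postoperative arrhythmia | Yes | Not stated; the word for occurrence may imply it | Comorbidity history only |
| Insulin infusion | Yes | No; use while on drug is a state | No; diabetes type only |

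A comorbidity entry for arrhythmia does not show which rhythm was present at drug start. A diabetes entry does not show whether an insulin infusion was running.

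**Step 2. Check whether relatedness removes these cases.** An event can be classed Not Related if another cause is most plausible, or if "a clinically plausible temporal sequence is inconsistent with the onset of the event relative to initiation of study drug". A condition that predates the drug fits this. Section 11.0 continues: "For reporting purposes, both 'Possibly Related' and 'Probably Related' will be considered" related. So a pre-existing condition need not be reported as related. The endpoint definitions in 6.0 and 11.0, however, are stated without regard to relatedness, so the raw incidence still contains it.

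**Step 3. Check the halting criteria.** The Grade 4 and Grade 5 criteria require relatedness. The Grade 3 criterion does not: "20% of the participants at time of analysis experience the same Grade 3 adverse event". At the four reviews, 20% is 0.20 × 5 = 1, 0.20 × 10 = 2, 0.20 × 15 = 3 and 0.20 × 20 = 4 patients.

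**Step 4. Size of the effect on incidence.** The plan states no figure for this, so there is none to reproduce. Inputs: n = 20 treated patients (section 5.0), and a proportion p with the condition present at drug start. The documents do not give p; 5%, 10% and 20% are assumed. The calculation takes all 20 patients as the denominator, treats patients as independent, and counts every such patient.

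- One carried-over patient adds 1/20 = 5 percentage points.
- Expected carried-over count = 20p.
- Chance of at least one = 1 − (1 − p)^20.

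| Assumed p | 20p | 1 − (1 − p)^20 |
|---|---|---|
| 5% | 1 | 1 − 0.95^20 = 0.64 |
| 10% | 2 | 1 − 0.90^20 = 0.88 |
| 20% | 4 | 1 − 0.80^20 = 0.99 |

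These are ceilings for one endpoint. A history of intermittent arrhythmia need not be present during the infusion. The phase-specific arrhythmia endpoints may also have fewer than 20 patients. With m patients the expected count falls to m × p, while each case adds 100/m points, which is more than 5 when m is below 20.

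**Step 5. Worst case for the Grade 3 criterion.** Suppose every carried-over case were graded 3 and the reviews took place at 5, 10, 15 and 20 treated patients. The chance of reaching 20% at one or more reviews would then be 0.25, 0.49 and 0.83 for p = 5%, 10% and 20%. At the first review alone it is 1 − (1 − p)^5 = 0.23, 0.41 and 0.67. If none is graded 3, the chance from this source is zero.

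**The case against.** A reader might infer that a recipient in chronic atrial fibrillation will be scored as having an adverse event caused by the study drug. The documents do not support that. The relatedness definitions allow a pre-existing condition to be classed Not Related, and the summary given to the DSMB must show relatedness and grade. For postoperative arrhythmia, the words for incidence and occurrence can fairly be read as meaning new events, so that text is ambiguous rather than an instruction to count prevalent rhythms.

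A reader might also infer that a patient treated in both phases is double-counted. The patient could appear in both phase-specific rates, but the plan defines no total that adds them.

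It can also be said that the baseline arrhythmia field allows affected patients to be identified at reporting, and that the percentages above overstate the likely effect. Both points are fair. The field gives only a history, and the percentages rest on an assumed prevalence and are upper bounds.

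The core of the concern still stands. For insulin the literal reading includes infusions already running, and the protocol lists no field to separate them. The intraoperative arrhythmia definition has no on-drug limit. Relatedness depends on the timing of onset, yet pre-dose rhythm and insulin status are not among the listed variables. If two readings of the postoperative endpoint are possible, two abstractors can score the same chart differently.

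**Conclusion.** The point holds as a gap in endpoint definition. Pre-existing conditions can enter the raw incidence reported for the secondary objective: plainly for insulin infusion, by omission of a time limit for intraoperative arrhythmia, and by ambiguity for postoperative arrhythmia. Under assumed prevalences at drug start of 5% to 20%, the carried-over count in 20 patients is at most 1 to 4 in expectation. The true size cannot be known from the documents. The effect on halting is conditional: it arises only through the Grade 3 criterion, and only if the carried-over event is graded 3. The plan does not require such events to be attributed to the drug. The correction is worth making before data collection, because pre-dose status may be hard to reconstruct from charts afterwards.

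**What to change.** In sections 6.0 and 11.0:

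1. Define both arrhythmia endpoints as new-onset arrhythmia, or documented worsening, after the first dose of study drug, relative to the last rhythm recorded before that dose.
2. Count an insulin infusion only if it was started after the first dose.
3. Add two fields to data collection: rhythm, and insulin-infusion status, each immediately before the first dose.
4. Report patients with the condition before the first dose in a separate row of the safety table and of the summary sent to the DSMB.

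A single per-patient arrhythmia incidence across the intraoperative and postoperative phases would be a useful addition but is optional.

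The cost is definition wording and a small chart abstraction for at most 20 patients; clinical care does not change. The drawback is some judgement about what counts as worsening, which a short written rule for abstractors would limit.

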7.0 EXPECTED RISKS/BENEFITS

The main anticipated benefit is the potential to establish improved hypotension management of future kidney transplant recipients at UIHHSS. This study could also potentially lead to further outcome studies on the effect vasopressors have on post-operative kidney transplant patients or studies directly comparing individual agents. Conversely, the expected risks are low given the existing data in critically ill patients with septic or other distributive shock. In the ATHOS-3 trial patients, the majority of patients evaluated were septic shock patients with a far greater severity of illness than kidney transplant recipients. In that investigation, there were no lifethreatening ADE's and minimal that were greater than placebo: most common ADE (> 4% and > 1.5 x placebo) being: thromboembolic events, thrombocytopenia, tachycardia, fungal infection, delirium, acidosis, hyperglycemia, and peripheral ischemia. With all medications, there are risks of adverse reactions. All adverse reactions that occur at an incidence of greater than 4% (and > 1.5 x placebo) in the prescribing information will be discussed individually with the subject prior to informed consent. These data points will be collected as noted above in the data collection section. There is also the risk of poorer outcomes and overall health with this agent. As with all investigations, there is a risk of breach of PHI. However, this risk is very low due to the numerous safeguards in place as described above and from using data collection in Redcap. Additionally, password protection and the hospital firewall security further reduce the likelihood of breach of information.

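### The thrombosis endpoint names imaging as its only source, but no scan is scheduled and imaging status is not recorded, so the reported incidence can be too low

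*Combined protocol and SAP*

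**What the plan says.** Section 6.0 (Safety data points) lists the thrombosis endpoint as "incidence of venous or arterial thrombosis occurring during the hospitalization for kidney transplant (captured by ultrasound or other diagnostic imaging". Section 11.0 repeats it in the same words.

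The other clinical events in that list have wider sources. Arrhythmia may be "confirmed via EKG, flowsheet, or note documentation". Ischemia is recorded as "incidence of digital or other peripheral/visceral ischemia occurring during hospitalization for kidney transplant (as noted in chart documentation". Fungal infection and delirium rest on the care team's documentation.

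On how events come to be looked for, 6.0 says "Patients will be monitored according to standard monitoring for patients in the peri-operative transplant and collection of ADE will focus on those found in" earlier studies of the drug, and closes the list with "All of the noted safety variables above are routinely monitored for as part of ICU care". On data capture it says "Health and laboratory data will be extracted manually from the electronic medical records". No section schedules an ultrasound or other scan, and none of the listed data items records whether a patient was imaged. A caveat about missing assessments is given for one safety variable only: "pH values in the ICU at 24hrs, 48hrs, and 72hrs (if available".

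Section 7.0 names the drug's most common adverse events as "thromboembolic events, thrombocytopenia, tachycardia, fungal infection, delirium, acidosis, hyperglycemia, and peripheral ischemia". Thromboembolism comes first. Section 3.0 makes the incidence of these events the secondary objective, and under 11.0 the DSMB reviews the collected safety endpoints after 5, 10, 15 and 20 subjects.

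**The concern.** A safety incidence is only as good as the rule that decides what counts. Here that rule has two gaps.

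- **Thrombosis proven without a scan.** A graft-vessel clot found at operation or on pathology is at least as certain as one seen on ultrasound, yet it does not fit the definition. Two data extractors could score it differently.
- **Patients never imaged.** Every treated patient is in the denominator. With imaging status unrecorded, 'no thrombosis seen on a scan' and 'no scan done' look the same in the dataset.

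Both gaps push the incidence down, and the event affected is a risk the protocol itself lists for the drug. There is also a consequence for monitoring. If clots proven by different routes are filed under different headings, events that belong together may not be added together when the halting rules are applied.

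**Working it through.** **The plan's own figure.** No thrombosis rate, imaging rate, power or alpha is stated, and 12.0 says the sample is one of convenience. The one figure that can be reproduced is the denominator: 20 treated / 0.50 vasopressor use (13.1) = 40 consented, as 5.0 and 13.1 state. The incidence will therefore be over 20 patients.

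**The text side by side (6.0 and 11.0).**

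| Event | Accepted source | Window |
|---|---|---|
| Arrhythmia | EKG, flowsheet or note | Intraoperative if dosed then; postoperative while on drug |
| Ischemia | Chart | Hospitalization |
| Fungal infection | Care team | To discharge |
| Delirium | Care team | While on drug |
| Thrombosis | Imaging | Hospitalization |

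The contrast within one list makes it natural to read the imaging phrase as a criterion and not as an example.

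**Illustration of under-capture.** Two inputs are assumed because the documents give neither: true risk *p* (5% to 20%) and share *s* of true events with a qualifying image (25% to 100%). The recorded risk is *q = p × s*, and the chance of reporting zero in 20 is (1 − *q*)^20.

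| *p* | *s* = 100% | 75% | 50% | 25% |
|---|---|---|---|---|
| 5% | 35.8% | 46.6% | 60.3% | 77.8% |
| 10% | 12.2% | 21.0% | 35.8% | 60.3% |
| 20% | 1.2% | 3.9% | 12.2% | 35.8% |

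For *p* = 10% and *s* = 50%: *q* = 0.05, expected recorded events fall from 20 × 0.10 = 2.0 to 20 × 0.05 = 1.0, and the chance of zero rises from 0.90^20 = 0.122 to 0.95^20 = 0.358.

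**Why the number not imaged matters.** With 0 events in 20, the exact two-sided 95% upper limit is 1 − 0.025^(1/20) = 16.8%. If only 10 had been imaged and the other 10 told us nothing, it would be 1 − 0.025^(1/10) = 30.8%. A reader who is not told the number imaged cannot judge how reassuring 0 of 20 is. The second figure shows lost information; it is not a rate to report.

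**Halting rules (11.0).** One rule needs the same related Grade 4 event in two participants; another needs the same Grade 3 event in 20% of participants, which is 1, 2, 3 or 4 at reviews of 5, 10, 15 or 20. Suppose two related Grade 4 graft thromboses occur, one seen on ultrasound and one found at operation and filed as visceral ischemia. Counted together they are 2 and meet the rule. Counted apart they are 1 and 1 and do not.

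**The case against.** The strongest reply is that the protocol never says a clot counts only if imaged, and gives no scoring rule for patients without a scan. The imaging phrase may be no more than a note of where data will be found, and the protocol's stated basis for ascertainment is that all these variables are "All of the noted safety variables above are routinely monitored for as part of ICU care". This has force: some scans probably happen in practice, and exclusion is an inference from the wording. But that sentence names no scan or time, the endpoint runs to discharge and not only through the ICU stay, and it does nothing for a clot proven without imaging. If wider capture was intended, the text should say so.

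A second reply is that the DSMB is protected elsewhere. Section 11.0 assesses relatedness for any adverse event, grades events by CTCAE, and only focuses collection on listed events. A clot found at operation could arrive as a graded event or as visceral ischemia. This stands, and it limits the monitoring concern to how events are labelled and counted together.

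A third is that imaging confirmation protects specificity in a small uncontrolled pilot. That is a fair reason not to mix unconfirmed clinical diagnoses into the main count. It is no reason to leave out operative or pathological proof.

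A reader might go further and infer that one missed case decides a halting rule. The documents do not support that. One Grade 3 case in 5 does reach 20%, but a clot sent straight back to surgery fits the protocol's description of Grade 4, where urgent intervention is indicated. That rule needs two related events. At an assumed 10% risk the chance of two or more thromboses in 5 patients is 1 − 0.9^5 − 5 × 0.1 × 0.9^4 = 8%, even with full capture and before any requirement on grade or relatedness.

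A reader might also infer that thrombosis has the narrowest ascertainment of all the endpoints, or that the cases missed are the most severe. Thrombocytopenia also has a single source, a platelet cut-off, and counts only during dosing. The severity of unimaged cases is plausible reasoning that nothing in the documents establishes.

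**Conclusion.** The concern holds as a gap in the endpoint definition and in the data list. As written, the thrombosis incidence can be too low because proof by operation or pathology is not an accepted source and because unimaged patients cannot be identified. The direction is clear; the size cannot be computed from the documents. The rise from 12% to 36% in the chance of reporting zero rests on an assumed 10% risk, an assumed 50% capture and independent patients, and it pools both gaps, so it is not the amount the fix would recover. For monitoring, the supportable conclusion is that like events could be split between labels under the two rules that count repeats; the documents do not show that they would be hidden from the DSMB. This should be changed because the listed risk is central to the safety objective and the change is small.

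**What to change.** In 6.0 and 11.0, define thrombosis as established by diagnostic imaging, operative finding or pathology. Record cases that were clinically diagnosed and treated without such confirmation as a separate category, shown beside the confirmed count.

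Add extracted fields for site (graft vessel, dialysis access, other), basis of diagnosis, and 'vascular imaging performed during hospitalization (Y/N)'.

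Report incidence over all treated patients, with the number not imaged stated next to it. Do not present a rate over imaged patients as an incidence: where scans follow clinical suspicion, that group is enriched for cases and the rate is biased upward. In the DSMB summary, list all thromboses together whatever the basis of proof.

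The cost is one definition sentence in two places and a few chart-extracted fields, with no added scans. The downside is some less certain diagnoses, kept visible by the separate category. Clots that are silent and never imaged stay uncounted; whether to schedule imaging is a clinical decision for the investigators.

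### Thrombosis, ischemia and fungal infection are counted only to discharge, with no stay or onset day listed; a supplementary day-30 count from the same chart is a cheap improvement

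*Combined protocol and SAP*

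**What the plan says.** The secondary objective (3.0) is safety, judged by the incidence of adverse events known from other Ang II studies. The safety data points in 6.0, repeated in 11.0, define three of these by the admission:

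- Thrombosis: "incidence of venous or arterial thrombosis occurring during the hospitalization for kidney transplant (captured by ultrasound or other diagnostic imaging".
- Ischemia: "incidence of digital or other peripheral/visceral ischemia occurring during hospitalization for kidney transplant (as noted in chart documentation".
- Fungal infection: "incidence of post-operative fungal infections prior to discharge (as documented by the clinical care team".

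Section 6.0 adds: "All of the noted safety variables above are routinely monitored for as part of ICU care".

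The variable lists in 6.0 contain the duration of Ang II, daily and discharge creatinine, kidney function at 1 and 3 months, calcineurin inhibitor levels to 6 months and renal replacement therapy in the first year. They do not contain length of stay, discharge day, first-dose day or event onset day. All data are read manually from the electronic record.

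Section 11.0 has the researchers judge causality: "Relationship of any AE to the use of study drug will be based on available information". The DSMB reviews the listed safety endpoints after 5, 10, 15 and 20 subjects.

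**The concern.** A window that closes at discharge has a different length for each patient. The resulting incidence pools patients with unequal follow-up, and without a discharge day or onset day nobody can later say how unequal it was, or restrict the count to a common window.

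The kidney outcomes are followed well past discharge, but the vascular events that could explain them are not. If a graft vessel thromboses after discharge, the plan would record a worse 1- or 3-month creatinine or GFR, or dialysis, but not why. Section 2 says there are no Ang II data in this population, so in a 20-patient pilot each such event carries information.

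What is at stake is how well the safety counts can be interpreted. The primary endpoint, time to the blood pressure goal, is not touched.

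**Working it through.** **1. Denominator.** Section 13.1 expects 40 consented so that 20 receive drug, at about 50% vasopressor use: 20 / 0.50 = 40, which reproduces. Each safety incidence therefore has a denominator of at most 20. No sample size calculation was done (12.0).

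**2. Windows side by side (6.0).**

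| Item | Collected until |
|---|---|
| Thrombosis, ischemia | end of transplant admission |
| Fungal infection | discharge |
| Creatinine, CrCl, GFR | 1 and 3 months |
| Calcineurin inhibitor level | 6 months |
| Renal replacement therapy | 1 year |

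The 1-month values already require the chart to be opened close to day 30.

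**3. Start of the window.** Ang II may first be given after surgery (6.0, After Transplant). The in-hospital counts are tied to the admission and not to first dose, so they can include an event that preceded the drug. A count from first dose to day 30 is therefore not simply the in-hospital count plus later events, and both must be shown.

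**4. Possible size (illustration; every input assumed).** Take a 30-day risk r per event type of 2%, 5% or 10%. Expected events in 20 patients are 20r = 0.4, 1.0 or 2.0.

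*Front-loaded timing.* With stay L and mean event time m in days, the share captured in hospital is (1 − exp(−L/m)) / (1 − exp(−30/m)).
- Lowest case, L = 4, m = 10: 0.347.
- Highest case, L = 10, m = 3: 0.964.

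Missed events are 20r × (1 − share):

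| r | Share 0.964 | Share 0.347 |
|---|---|---|
| 2% | 0.014 | 0.261 |
| 5% | 0.036 | 0.653 |
| 10% | 0.071 | 1.306 |

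*Constant hazard, probably too pessimistic.* At r = 10%, events expected in hospital are 20 × (1 − 0.90^(L/30)): 0.21 for L = 3 and 0.96 for L = 14. Missed: 2.0 − 0.21 = 1.79 and 2.0 − 0.96 = 1.04.

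**5. Precision.** Exact (Clopper-Pearson) 95% intervals: 0/20 gives 0% to 16.8%; 1/20 gives 0.1% to 24.9%; 2/20 gives 1.2% to 31.7%. One recovered event does not make a rate precise.

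**6. Contact with the halting rule (11.0).** One criterion is "20% of the participants at time of analysis experience the same Grade 3 adverse event". It is met by 0.20 × 5, 10, 15, 20 = 1, 2, 3, 4 participants. If the whole assumed 30-day risk were Grade 3 and fully observed, the chance of meeting it at five subjects is 1 − (1 − r)^5 = 9.6%, 22.6% or 41.0%. Much of that exists already: at r = 10%, in-hospital events alone give 1 − (1 − 0.0347)^5 = 16.2% to 1 − (1 − 0.0964)^5 = 39.8%. These figures describe what could follow from counting more events. They do not show a flaw in the plan.

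**The case against.** The strongest defence is that an in-hospital window is a reasonable choice for a short infusion. It is labelled as such, it matches where monitoring happens, and late events are hard to attribute, fungal infection under immunosuppression above all. That stands, and it is why the point is an improvement only.

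Timing is also not wholly ignored. The relatedness definitions in 11.0 consider onset relative to the start of drug, and the researchers undertake to seek enough information to judge it. Daily creatinine traces the stay roughly. That stands in part: onset is sought for a causality judgement but is not a listed variable, and a run of laboratory values is a poor substitute for a discharge day.

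A reader might take the reference to any AE in 11.0 as open-ended collection. That sentence concerns attribution. The list that defines capture is windowed, and 13.3 deals with unforeseen problems, whereas these events are foreseen.

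A reader might also infer that follow-up differs for reasons tied to treatment, since section 2 links catecholamines with longer stay and 6.0 leaves added vasopressors to clinicians. This is a possibility only. The documents give no stay data, and no planned comparison of these events depends on it.

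Finally, step 6 might tempt a reader to exempt post-discharge events from the 20% Grade 3 criterion. That criterion states no time limit and no relatedness requirement, so an exemption would narrow a safety rule: four of 20 patients readmitted with Grade 3 thrombosis would no longer trigger a halt. The documents give no ground for that trade.

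**Conclusion.** The point holds as a minor, inexpensive improvement. The three windows do close at discharge, stay and onset are not listed variables, and the chart is already read at 1 month.

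The documents do not support reading this as a biased endpoint or an established undercount. They give no event rates, lengths of stay or event timing, so the 0.01 to 1.8 missed events per type rests entirely on the assumed 2% to 10% risk, 3- to 14-day stay and the two timing models. All 20 patients receive Ang II, so no between-arm bias arises. Nor would a day-30 count solve ascertainment: routine ICU monitoring ends with ICU care, and later events are found only if imaged or written down in this record. The gain is a common window, a link to the later kidney outcomes and fewer lost single events. Precision at 20 patients does not change materially.

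**What to change.** In 6.0 and 11.0:

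- Keep the in-hospital counts as defined, and flag any event that occurred before first dose.
- Add first-dose day, discharge day and event onset day, stored as days from transplant. Calendar dates would sit badly with the commitment that the REDCap data contain no PHI.
- Add a supplementary count of thrombosis (with site: graft vessel or other), peripheral or visceral ischemia and fungal infection, from first Ang II dose to day 30 after that dose. Read it from notes and imaging at the 1-month extraction, once day 30 has passed.
- Report it as n/N beside the in-hospital n/N, stating that post-discharge events are found only if imaged or documented in this record.
- Give the DSMB the day-30 count descriptively at each review, with N = subjects who have reached day 30 or died. Leave all halting criteria as written.

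The cost is a protocol amendment, a few REDCap fields and extra chart review for at most 20 subjects; no added visit or test. The downsides are weaker attribution of late events and missed events treated elsewhere, which is why the new count supplements the in-hospital one and does not replace it. If only one step is taken, the three day fields are the smallest useful version.
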